11. STUDY TERMINATION

The occurrence of one or more Unanticipated Serious Adverse Device Effect (USADE), or any SAE where the relationship to study agent cannot be ruled out, may result in stopping further dispensing of test article. In the event of a USADE or SAE, the Sponsor may unmask the treatment regimen for the subject(s) and will discuss this with the Investigator before any further subjects are enrolled.

The Sponsor will determine when a study will be stopped. The Principal Investigator always has the discretion to initiate stopping the study based on patient safety or if information indicates the study's results are compromised.

JJVC reserves the right to terminate the study at any time for any reason. Additionally, the IEC/IRB reserves the right to terminate the study if an unreasonable risk is determined. The study can be terminated by the Principal Investigator at the individual clinical site due to specific clinical observations, if in their opinion, after a discussion with JJVC, it is determined that it would be unwise to continue at the clinical site.

JJVC (and the IEC/IRB and DMC, if applicable) will evaluate all adverse events. If it is determined that an adverse event presents an unreasonable risk, the investigation, or that part of the investigation presenting the risk, will be terminated, as soon as possible.

Should the study be terminated (either prematurely or as scheduled), the Investigator will notify the IEC/IRB and Regulatory Authority as required by local regulatory requirements.

12. PROCEDURE FOR HANDLING PRODUCT QUALITY COMPLAINTS

A Product Quality Complaint (PQC) refers to any written, electronic, or oral communication that alleges deficiencies related to the identity, quality, durability, reliability, safety, effectiveness or performance of test articles after they have been released for clinical trial use.

Potential complaints may come from a variety of sources including but not limited to subjects, clinical research associates (CRA), clinical operations managers (COM), medical monitors, and site personnel, etc. The following are not considered product quality complaints:

- Subject satisfaction inquiries reported via "Subjective Questionnaires" and "Patient Reported Outcomes (PRO)"
- Clinical test articles that are stored improperly or damaged after receipt at the investigational site
- Lens replacements that occur due to drops/fall-outs
- Damage deemed by clinicians or clinical staff to be caused by handling by the user, and not indicative of a quality deficiency (i.e. tears, rips, etc.), only in situations where there is no deficiency alleged by the subject

Within 24 hours of site personnel becoming aware that a PQC has occurred, the PQC must be recorded in the EDC system, which will trigger an automatic email notification to the appropriate COM/CRA and Clinical QA representative. In cases where the EDC system in use is not configured to send automatic notifications or when an EDC system is not used, the COM/CRA is responsible for notifying Clinical QA upon discovery that a PQC has occurred.

Upon receipt of the EDC notification, the COM/CRA will contact the study site to collect additional information which will include:

- Date the complaint was received/recorded in the EDC System (Date of Sponsor Awareness)
- Who received the complaint
- Study number
- Clinical site information (contact name, site ID, telephone number)
- Lot number(s)
- Unique Subject Identifier(s)
- Indication of who first observed complaint (site personnel or subject)
- OD/OS indication, along with whether the lens was inserted
- Any related AE number if applicable
- Detailed complaint description (scheduled/unscheduled visit, wear time, symptoms, resolution of symptoms, etc.)
- Eye Care Provider objective (slit lamp) findings if applicable
- Confirmation of product availability for return (and tracking information, if available), or rationale if product is not available for return

Once a complaint is received, it will be assessed by the COM, CRA, or trained site personnel to determine if it is an Adverse Event/Serious Adverse Event (AE/SAE). If the complaint results in an AE/SAE, the COM/CRA, or trained site personnel will follow Section 13 of this

protocol. If the AE/SAE was potentially the result of a product quality related deficiency, these procedures also applies and will be executed in parallel.

In some cases, a PQC form may be generated in EDC by the site in error. In this event, the PQC forms will be marked "Intentionally Left Blank" or "ILB". Justification for ILB must be documented.

13. ADVERSE EVENTS

13.1. Definitions and Classifications

Adverse Event (AE) – An AE is "any untoward medical occurrence, unintended disease or injury, or untoward clinical signs (including abnormal laboratory findings) in subjects, users or other persons, whether or not related to the investigational medical device.

Note 1 to entry: This definition includes events related to the investigational medical device or the comparator.

Note 2 to entry: This definition includes events related to the procedures involved.

Note 3 to entry: For users or other persons, this definition is restricted to events related to investigational medical devices."

An AE includes any condition (including a pre-existing condition) that:

- 1. Was not present prior to the study, but appeared or reappeared following initiation of the study
- 2. Was present prior to the study, but worsened during the study. This would include any condition resulting from concomitant illnesses, reactions to concomitant medications, or progression of disease states
- 3. Pregnancy must be documented as an adverse event and must be reported to the clinical monitor and to the Sponsor immediately upon learning of the event

Serious Adverse Event (SAE) – An SAE is any untoward medical occurrence that:

- Results in death
- Is life threatening
- Requires in-patient hospitalization or prolongation of existing hospitalization
- Results in persistent or significant disability/incapacity (e.g., a sight threatening event, a significant persistent or permanent change, impairment, damage, or disruption to the subject's body)
- Is a congenital anomaly/birth defect, or
- Requires intervention to prevent permanent damage (the use of the test article resulting in a condition which requires medical or surgical intervention to preclude permanent impairment of the body structure or a body function). Important medical events that may not result in death, be life-threatening, or require hospitalization may be considered an SAE when, based upon appropriate medical judgment, they may jeopardize the patient or subject and may require medical or surgical intervention to prevent one of the outcomes listed in the above definition

Diagnoses and conditions that are considered Ocular Serious Adverse Events include, but not limited to:

- Microbial Keratitis (MK)
- Iritis (including cells in the anterior chamber)
- Permanent decrease in best spectacle corrected visual acuity (BSCVA) equivalent to 2 acuity lines or greater
- Central Corneal Opacity
- Central Corneal Neovascularization
- Uveitis
- Endophthalmitis
- Hypopyon
- Hyphemia
- Penetration of Bowman's Membrane
- Persistent Epithelial Defect
- Limbal cell Damage leading to Conjunctivalization

Significant Adverse Events – Those events that are usually symptomatic and warrant discontinuation (temporary or permanent) of the test article (excluding Serious Adverse Events).

Diagnoses and conditions that are considered Ocular Significant Adverse Events include, but not limited to the following:

- Contact Lens Induced Peripheral Ulcer (CLPU)
- Significant Infiltrative Events (SIE)
- Superior Epithelial Arcuate Lesions (SEALs)
- Any Temporary Loss of >2 Lines of BSCVA
- Other grade 3 or higher corneal findings, such as abrasions or edema
- Non-contact lens related corneal events e.g. Epidemic Keratoconjunctivitis (EKC)
- Asymptomatic Corneal Scar
- Any corneal event which necessitates temporary lens discontinuation >2 weeks

Non-Significant Adverse Events – Those conditions that are usually asymptomatic and usually do not warrant discontinuation (temporary or permanent) of the test article. However, the Investigator may choose to treat as a precautionary measure.

Diagnoses and conditions that are considered Ocular Non-Significant Adverse Events include, but not limited to the following:

- Non-significant Infiltrative Event (NSIE)
- Contact Lens Papillary Conjunctivitis (CLPC)
- Superficial Punctate Keratitis (SPK)
- Conjunctivitis: Bacterial, Viral, Allergic
- Blepharitis
- Meibomianitis
- Contact Dermatitis
- Localized Allergic Reactions

• Any corneal event not explicitly defined as serious or significant adverse event, which necessitates temporary lens discontinuation <2 weeks

Adverse Device Effect (ADE) – An ADE is an "adverse event related to the use of an investigational medical device.

Note 1 to entry: This definition includes adverse events resulting from insufficient or inadequate instructions for use, deployment, implantation, installation, or operation, or any malfunction of the investigational medical device.

Note 2 to entry: This definition includes any event resulting from use error or from intentional misuse of the investigational medical device."

Unanticipated Adverse Device Effect (UADE) – Any serious adverse effect on health or safety or any life-threatening problem or death caused by, or associated with, the test article, if that effect, problem, or death was not previously identified in nature, severity, or degree of incidence in the investigational plan, Investigator's Brochure or protocol, or any other unanticipated serious problem associated with the test article that relates to the rights, safety and welfare of subjects.

13.2. Assessing Adverse Events

In conjunction with the medical monitor, the Investigator will evaluate adverse events to ensure the events are categorized correctly. Elements of categorization will include:

- Seriousness/Classifications (see definition in Section 13.1)
- Causality or Relatedness i.e. the relationship between the test article, study treatment or study procedures and the adverse event (not related; unlikely related; possibly related; related see definition in Section 13.2.1)
- Adverse Event Severity Adverse event severity is used to assess the degree of intensity of the adverse event (mild; moderate; severe for all events see definition in Section 0)
- Outcome not recovered or not resolved; recovering or resolving; recovered or resolved with sequelae; recovered or resolved; death related to adverse event; unknown
- Actions Taken none; temporarily discontinued; permanently discontinued; other

13.2.1. Causality Assessment

Causality Assessment – A determination of the relationship between an adverse event and the test article. The test article relationship for each adverse event should be determined by the investigator using these explanations:

- Not Related- An adverse event that is not related to the use of the test article, study treatment or study procedures
- Unlikely Related An adverse event for which an alternative explanation is more likely, e.g. concomitant treatment, concomitant disease(s), or the relationship of time suggests that a causal relationship is not likely
- Possibly Related An adverse event that might be due to the use of the test article, or to the study treatment or study procedures. An alternative explanation, e.g.

- concomitant treatment, concomitant disease(s), is inconclusive. The relationship in time is reasonable. Therefore, the causal relationship cannot be excluded
- Related An adverse event that is listed as a possible adverse effect (device) or adverse reaction (drug) and cannot be reasonably explained by an alternative explanation, e.g. concomitant treatment of concomitant disease(s). The relationship in time is very suggestive, e.g. it is confirmed by de-challenge and re-challenge

13.2.2. Severity Assessment

Severity Assessment – A qualitative assessment of the degree of intensity of an adverse event as determined by the Investigator or reported to him/her by the subject. The assessment of severity is made irrespective of test article, study treatment or study procedure relationship or seriousness of the event and should be evaluated according to the following scale:

- Mild Event is noticeable to the subject, but is easily tolerated and does not interfere with the subject's daily activities
- Moderate Event is bothersome, possible requiring additional therapy, and may interfere with the subject's daily activities
- Severe Event is intolerable, necessitates additional therapy or alteration of therapy and interferes with the subject's daily activities

13.3. Documentation and Follow-Up of Adverse Events

The recording and documenting of adverse events (ocular and non-ocular) begins when the subjects are exposed to the test article, study treatment or study procedure. Adverse events reported before the use of test article, start of study treatment, or study procedures will be recorded as medical history. However, if the condition deteriorates at any time during the study it will be recorded and reported as an AE. Untoward medical events reported after the subject's exit from the study will be recorded as adverse events at the discretion of the Investigator.

Upon finding an adverse event, the Principal Investigator will document the condition in the subject record and in the eCRFs. He/she will complete the Adverse Event /eCRF.

Complete descriptions of all adverse events must be available in the subject record. All Adverse Events including local and systemic reactions not meeting the criteria for "serious adverse events" shall be captured on the appropriate case report form or electronic data system. All adverse events occurring while the subject is enrolled in the study must be documented appropriately regardless of relationship.

It is the Investigator's responsibility to maintain documentation of each reported adverse event. All adverse events will be followed in accordance with applicable licensing requirements. Such documentation will include the following:

- Adverse event (diagnosis not symptom)
- Drawings or photographs (where appropriate) that detail the finding (e.g., size, location, and depth, etc.)
- Date the clinical site was notified
- Date and time of onset

- Date and time of resolution
- Adverse event classification, severity, and relationship to test articles, as applicable
- Treatment regimen instituted, including concomitant medications prescribed, in accordance with applicable licensing requirements
- Any referral to another health care provider if needed
- Outcome, ocular damage (if any)
- Likely etiology
- Best corrected visual acuity at the discovery of the event and upon conclusion of the event

In addition, if an infiltrate(s) is present, he/she will complete the Corneal Infiltrate Assessment eCRF. Where necessary, a culture of the corneal lesion will be collected to determine if the infection is microbial in nature. If cultures are collected, the date of culture collection and laboratory utilized will be recorded.

Changes in the severity of an AE shall be documented to allow an assessment of the duration of the event at each level of intensity to be performed. Adverse events characterized as intermittent require documentation of the onset and duration of each episode. Changes in the assessment of relationship to the Test Article shall also be clearly documented.

Subjects who present with an adverse event shall be followed by the Investigator, within licensure, until all signs and symptoms have returned to pre-treatment status, stabilized, or been satisfactorily resolved. If further treatment beyond licensure is required, the patient will be referred to the appropriate health care provider. The Investigator will use his/her clinical judgment as to whether a subject reporting with an adverse event will continue in the study. If a subject is discontinued from the study, it will be the responsibility of the Investigator to record the reason for discontinuation. The Investigator will also document the adverse event appropriately and complete the Adverse Event eCRF. Any subjects with ongoing adverse events related to the test article, study treatment or study procedures, as of the final study visit date, should be followed to resolution of the adverse event or until referral to an appropriate health care provider, as recommended by the Investigator. Non-ocular adverse events that are not related to the test article, study treatment, or study procedures may be recorded as "ongoing" without further follow-up.

13.4. Reporting Adverse Events

The Investigator will notify the Sponsor of an adverse event by e-mail, facsimile, or telephone as soon as possible and no later than 24 hours from discovery for any serious /significant adverse events, and 2 days from discovery for any non-significant adverse event. In addition, a written report will be submitted by the Principal Investigator to the IEC/IRB according to their requirements (Section 13.4.2). The report will comment whether the adverse event was considered to be related to the test article, study treatment or study procedures.

13.4.1. Reporting Adverse Events to Sponsor

Serious/Significant Adverse Events

The Investigator will inform the sponsor of all serious/significant adverse events occurring during the study period as soon as possible by e-mail, fax, or telephone, but no later than 24 hours following discovery of the event. The Investigator is obligated to pursue and obtain information requested by the Sponsor in addition to that information reported on the eCRF. All subjects experiencing a serious/significant adverse event must be followed up and all outcomes must be reported.

When medically necessary, the Investigator may break the randomization code to determine the identity of the treatment that the subject received. The Sponsor and study monitor should be notified prior to unmasking the test articles.

In the event of a serious/significant adverse event, the Investigator must:

- Notify the Sponsor immediately
- Obtain and maintain in the subject's records all pertinent medical information and medical judgment for colleagues who assisted in the treatment and follow-up of the subject
- Provide the Sponsor with a complete case history which includes a statement as to whether the event was or was not related to the use of the test article
- Notify the IEC/IRB as required by the IEC/IRB reporting procedure according to national regulations

Unanticipated (Serious) Adverse Device Effect (UADE)

In the event of an Unanticipated (Serious) Adverse Device Effect (UADE), the Investigator will submit a report of the UADE to the Sponsor and IEC/IRB as soon as possible, but no later than 24 hours after the Investigator first learns of the effect. This report is in addition to the immediate notification mentioned above.

The Sponsor must conduct an evaluation of the UADE and must report the results of the evaluation to FDA, the IEC/IRB and participating Investigators within 10 working days after the Sponsor first receives notification of the effect.

Non-Serious Adverse Events

All non-serious adverse events, including non-serious adverse device effects, will be reported to the sponsor by the Investigator no later than 2 days from discovery.

13.4.2. Reporting Adverse Events to the Responsible IEC/IRB and Health Authorities

Adverse events that meet the IEC/IRB requirements for reporting must be reported within the IEC/IRB's written guidelines. Each clinical site will refer to and follow any guidelines set forth by their Approving IEC/IRB. Each clinical site will refer to and follow any guidelines set forth by their local governing Health Authorities.

The Sponsor will report applicable Adverse Events to the local health authorities according the written guidelines, including reporting timelines.

13.4.3. Event of Special Interest

Adverse events that meet the IEC/IRB requirements for reporting must be reported within the IEC/IRB's written guidelines. Each clinical site will refer to and follow any guidelines set forth by their Approving IEC/IRB. Each clinical site will refer to and follow any guidelines set forth by their local governing Health Authorities.

The Sponsor will report applicable Adverse Events to the local health authorities according the written guidelines, including reporting timelines.

13.5. Reporting of Pregnancy

Subjects reporting pregnancy (by self-report) during the study will be discontinued after the event is recorded as an Adverse Event. Once discontinued, pregnant participants and their fetuses will not be monitored for study related purposes. At the Investigator's discretion, the study participant may be followed by the Investigator through delivery. However, this data will not be collected as part of the clinical study database. Pregnant participants are not discontinued from contact lens or solution related studies for safety concerns, but due to general concerns relating to pregnancy and contact lens use. Specifically, pregnant women are discontinued due to fluctuations in refractive error and/or visual acuity that occur secondary to systemic hormonal changes, and not due to unforeseen health risks to the mother or fetus.

14. STATISTICAL METHODS

14.1. General Considerations

Statistical Analysis will be undertaken by the sponsor or under the authority of the sponsor. A general description of the statistical methods to be implemented in this clinical trial is outlined below.

All data summaries and statistical analyses will be performed using the SAS software Version 9.4, add/modify software if necessary (SAS Institute, Cary, NC). Throughout the analysis of data, the results for each subject/eye will be used when available for summarization and statistical analysis. Unscheduled visits will summarized separately and will be excluded from the statistical analysis.

Summary tables (descriptive statistics and/or frequency tables) will be provided for all baseline variables, efficacy variables and safety variables as appropriate. Continuous variables will be summarized with descriptive statistics (n, mean, standard deviation (SD), median, minimum and maximum). Frequency count and percentage of subjects or eyes within each category will be provided for categorical data.

14.2. Sample Size Justification

This study was designed and powered to show non-inferiority between the Test lens compared to the Control lens with respect to CLUE comfort and vision. It was assumed there was no difference between the Test and Control lenses. The sample size was calculated to achieve a minimum statistical power of 90% and a type I error of 5%.

The sample size calculation was based on historical data from a similar study, CR-5960 The Test lens from CR-5960 is the Control for this study. CR-5960 enrolled 133 subjects, of which 130 (97.7%) were dispensed study lenses. Of the dispensed subjects, 127 (95.5%) completed the study and 3 (2.3%) subjects were discontinued. The per-protocol population included 121 (91.0%) subjects out of the total 127 that completed. Table 4 summarizes CLUE scores from CR-5960 at the 2-week follow-up.¹³

Table 4: Descriptive CLUE scores from CR-5960 (Historical Data)

| CLUE Domain | Study Lenses | |
|-----------------------------------|------------------|---------------------------|
| | Acuvue Oasys | Solace – 25% differential |
| Comfort [mean (SD ¹)] | 61.185 (24.2024) | 64.339 (24.2132) |
| Vision [mean (SD ¹)] | 66.792 (20.0073) | 69.445 (20.1752) |

¹SD: Standard Deviation

Sample size calculation for CLUE comfort and vision were carried out using an approximation of the power of an F-test derived from the non-centrality parameter calculated form the observed F-statistic of a linear model. ¹⁴

Model details:

CLUE comfort and vision were analyzed separately using a linear mixed model. Lens type, was included as the only fixed effect. A compound symmetric (CS) covariance was used to model the correlation between measurements within the same subject across study periods. Below is the variance-covariance matrix used in the CLUE each model.

$$\sum_{comfort} \begin{pmatrix} 349.3 & 110.9 & 110.9 \\ 110.9 & 349.3 & 110.9 \\ 110.9 & 110.9 & 349.3 \end{pmatrix}$$

$$\sum_{vision} \begin{pmatrix} 257.4 & 82.1 & 82.1 \\ 82.1 & 257.4 & 82.1 \\ 82.1 & 82.1 & 257.4 \end{pmatrix}$$

Table 5: Sample Size Calculations for CLUE Comfort and Vision

| CLUE Domain | Number to Complete | Power (%) |
|--------------------|--------------------|-----------|
| Comfort | 50 | 77% |
| | 60 | 85% |
| | 80 | 93% |
| Vision | 50 | 88% |
| | 60 | 93% |
| | 80 | 98% |

Assuming no difference between the Test lens and Control lens, the sample size required to achieve non-inferiority with a minimum power of 90% and a type I error controlled at 5% was estimated to be 80 subjects.

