2.3. Hypotheses

Primary Hypotheses

| Primary Hypotheses | | |
|----------------------|------------------------------------------------------------------------------------------------------------------------------------------------------------------------------------|--|
| Endpoint | Hypothesis | |
| Overall CLUE Vision | The test lens will be non-inferior to the control lens at the 2-week follow-up with respect to CLUE overall quality of vision. A non-inferiority margin of -5 points will be used. | |
| Overall CLUE Comfort | The test lens will be non-inferior to the control lens at the 2-week follow-up with respect to CLUE overall comfort. A non-inferiority margin of -5 points will be used. | |

Both Primary hypotheses must be met for this study to be considered successful.

Other Hypotheses

| | Other Hypotheses | | | |
|---------------------------------|-------------------------------------------------------------------------------------------------------------------------------------------------------------------------------------------------------------------------------------------------------------------------------------------------------------------------------------------------------------------------------------------------------------------------|--|--|--|
| Endpoint | Hypothesis | | | |
| Outdoor Performance Measures | The test lens will be superior to the control lens in at least 2 of the following 4 outdoor performance measure(s) at the 2-week follow-up. An odds ratio margin of 1 will be used. 1. Ability to see comfortably in bright sunlight 2. Reduction in glare in bright sunlight 3. Reduction in squinting in bright sunlight 4. Reduction in eye strain in bright sunlight | | | |
| Driving Performance Metrics | The test lens will be non-inferior to the control lens in both of the following driving performance metrics at the 2-week follow-up. An odds ratio margin of 0.67 will be used. 1. Reduction in glare while driving during the day 2. Reduction in glare while driving during the night | | | |
| Indoor Performance Measures | The test lens will be superior to the control lens in at least 2 of the following 4 outdoor performance measure(s) at the 2-week follow-up. An odds ratio margin of 1 will be used. 1. Reduction in squinting while working on the computer 2. Reduction in glare from the computer screen 3. Reduction in glare caused by bright indoor lights 4. Reduction in glare caused by bright light coming through the window | | | |

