14.5. Primary Analysis

CLUE Comfort and Vision

Overall comfort and vision CLUE scores will be analyzed separately using a linear mixed model adjusting for baseline values as a covariate. Sequence of lens wear, period, lens type, first order carryover effect will be included in each model as fixed effects. An appropriate covariance structure will be used to model the residual errors between measurements within same subject across study periods (R-side). The covariance structure will be selected based on the finite-sample corrected Akaike's Information Criterion. Covariance structures considered include:

- Unstructured Covariance Structure (UN)
- Homogenous Compound symmetry (CS)
- Heterogeneous Compound Symmetry (CSH)
- Autoregressive first order (AR (1))

For autoregressive first order (AR (1)), Site and Subject nest within site will be included as random effects (G-side). For the remaining covariance structures only site will be included as a random effect (G-side). The Kenward and Roger method (Kenward and Roger, 1997) will be used for the denominator degree of freedom.

Comparisons between the test and control lens at the 2-weeks follow-up will be carried out using two-sided 95% confidence intervals constructed for least-square mean differences (test

minus control). The lower limit of the 95% confidence interval will be compared to -5 and 0 to test for non-inferiority and superiority, respectively. Non-inferiority of the test lens relative to the control will be concluded if a lower limit is above -5. If non-inferiority is established the superiority will be tested. Superiority will be declared if the lower limit of the 95% confidence interval is above 0.

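### Section 14.2's planning matrices contradict the CR-5960 variances in Table 4, and the stated 93%/98% power at 80 completers does not follow from the printed inputs

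*Combined protocol and SAP*

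**What the plan says.** Section 14.2 of the combined protocol and SAP sets the target: "The sample size was calculated to achieve a minimum statistical power of 90% and a type I error of 5"%. It names CR-5960 as the source of the planning data and assumes a zero true difference ("It was assumed there was no difference between the Test and Control lenses"). Table 4 prints the CR-5960 means and SDs at two weeks. Comfort is "61.185 (24.2024) | 64.339 (24.2132"); the vision SDs are 20.0073 and 20.1752.

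The model details then state "Lens type, was included as the only fixed effect", with compound symmetry across periods. The comfort matrix has the row "349.3 & 110.9 & 110.9"; the vision matrix has 257.4 on the diagonal and 82.1 off it. Table 5 gives comfort power of 77%, 85% and 93%, and vision power of 88%, 93% and 98%, at 50, 60 and 80 completers. The section concludes that "the sample size required to achieve non-inferiority with a minimum power of 90"% is 80 subjects.

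The margin is in Section 2.3 ("A non-inferiority margin of -5 points will be used"), which also requires both primary hypotheses to be met. Section 14.5 applies the lower limit of a two-sided 95% interval: "Non-inferiority of the test lens relative to the control will be concluded if a lower limit is above -5".

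**The concern.** In a model whose only fixed effect is lens type, the variance of one observation should be close to the within-lens variance of the raw scores. Table 4 supplies that variance, and the matrix diagonals fall well short of it. So the matrices did not come from the Table 4 data under the described model, or the model held terms that the text does not list, or the matrix entries are mislabelled.

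Table 5 is the only support for 80 completers and for the 90% minimum. In this crossover, power depends almost wholly on the within-subject variance, and the section leaves unclear which printed number that is. The margin for error is small. Even at the stated 93% and 98%, joint power could be as low as 0.93 + 0.98 − 1 = 0.91.

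**Working it through.** **Inputs.** Margin 5, true difference 0 and two-sided 95% interval (Sections 2.3, 14.2, 14.5); sequences Test/Control/Control and Control/Test/Test in blocks of two, hence 1:1 (Section 5.1); 80 completers in total (Sections 3.1, 4.1, 4.3); SDs and matrices from Section 14.2.

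**1. Variances implied by Table 4.**
- Comfort: (24.2024² + 24.2132²)/2 = 586.0
- Vision: (20.0073² + 20.1752²)/2 = 403.7

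**2. Comparison with the matrices.**
- Diagonals as printed: 349.3/586.0 = 0.596 (40% lower); 257.4/403.7 = 0.638 (36% lower).
- Diagonal plus off-diagonal, read as two variance components: 349.3 + 110.9 = 460.2, and 460.2/586.0 = 0.785 (21% lower); 257.4 + 82.1 = 339.5, and 339.5/403.7 = 0.841 (16% lower).

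The gap survives either reading.

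**3. Power formula.** Let *b* be the covariance and *w* the within-subject variance (diagonal minus off-diagonal). With lens coded (1,0,0) or (0,1,1), the within-subject sum of squares is 2/3. The subject mean lies 1/6 from its average, so 3 × (1/6)² = 1/12. Then

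Var(lens effect) = 1 / { N × [ 2/(3w) + 1/(12(w + 3b)) ] }

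Power comes from the noncentral t with noncentrality 5/SE and 2N − 1 degrees of freedom.

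**4. Printed matrices, 80 in total.**
- Comfort: w = 349.3 − 110.9 = 238.4, b = 110.9; SE = 2.061; noncentrality 2.426; power 67.4%.
- Vision: w = 257.4 − 82.1 = 175.3, b = 82.1; SE = 1.768; noncentrality 2.829; power 80.3%.

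**5. Which reading gives Table 5?**

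| Reading | Comfort at 50/60/80 (%) | Vision at 50/60/80 (%) |
|---|---|---|
| Table 5 as stated | 77 / 85 / 93 | 88 / 93 / 98 |
| Printed matrices, N total | 47.6 / 54.9 / 67.4 | 60.0 / 68.1 / 80.3 |
| 110.9 and 82.1 as within-subject residuals, N total | 78.1 / 85.2 / 93.5 | 88.9 / 93.7 / 98.1 |
| Printed matrices, N per sequence (2N in total) | 77.0 / 84.1 / 92.8 | 88.2 / 93.2 / 97.9 |

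The third row keeps the printed diagonals as totals. Using the summed totals instead changes the figures by at most about 0.2 points. The fourth row needs 160 completers, which conflicts with the 80 for the whole study. A one-sided 5% test with the printed matrices reaches only 78.0% and 87.9% at 80. Of the readings tried, only the residual reading fits 80 total subjects.

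**6. How the Table 4 gap bears on power.**
- Residual 110.9, all other Table 4 variance between subjects (b = 586.0 − 110.9 = 475.1): comfort power 93.3%.
- Residual 238.4 with the Table 4 total (b = 347.6): comfort power 66.2%.
- Using within-subject information only, as when sequence is fitted, Var = 1.5w/80 with 157 degrees of freedom. Residual 110.9 gives 93.1%, and residual 125.3 gives 90.0%.
- The 90% threshold is therefore a residual of about 125. It is about 127 if the small between-subject contribution is also used.

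**The case against.** The strongest reply is that Table 4 gives only marginal SDs, while the lens contrast rests on within-subject variance, about which Table 4 says nothing. A term such as the single Visit 1 baseline score is constant across a subject's periods, so adjusting for it would shrink the between-subject variance and leave the residual essentially unchanged. A random site effect would act in a similar way, and a statement about fixed effects does not exclude one. The matrices may also come from a different CR-5960 analysis set. Valid power does not require the components to add up to Table 4.

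All of that stands as an argument against inferring a power loss from Table 4. A reader might conclude that comfort power is really 86% or 76%, by scaling the residual up to the Table 4 total: 110.9 × 586.0/460.2 = 141.2, or 110.9 × 586.0/349.3 = 186.1. The documents do not support this. It assumes that 110.9 is the residual and that the residual grows in proportion to total variance. The second figure also treats the diagonal as the total while taking the off-diagonal as the residual, which is not how the printed matrix reads.

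The reply does not remove the contradiction. Section 14.2 names no baseline, site effect or separate analysis set for the planning model. It also does not explain why the printed matrices fail to give Table 5 at 80 subjects.

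**Conclusion.** The concern holds as an unreconciled conflict among printed planning inputs. The matrix diagonals are 40% (comfort) and 36% (vision) below the Table 4 variances, or 21% and 16% below if the entries are summed, and nothing stated accounts for it. Taken literally, the matrices give about 67% and 80% power with 80 total completers. Joint power would then be 0.674 × 0.803 = 54% if the endpoints were independent, and in any case between 0.674 + 0.803 − 1 = 48% and 67%. The stated 93%, 98% and 90% minimum therefore do not follow from what is printed.

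A reader might infer that the trial truly has 67% power. That goes too far, because the near-exact match when 110.9 and 82.1 are the residuals makes mislabelled matrices a plausible explanation. In that case comfort power is about 93% if the missing variance is wholly between subjects, and below 90% if the true comfort residual exceeds about 125. The documents do not give the CR-5960 within-subject variance in a form that decides this. All figures assume a zero true difference, 1:1 sequences, complete data and compound symmetry.

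**What to change.** In Section 14.2:

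- State which quantity is the within-subject residual variance from the CR-5960 fit, for each endpoint, and the between-subject variance beside it.
- Correct the matrices, or the sentence on fixed effects, so that they agree with Table 4. Otherwise name the covariate, random effect or analysis set that explains the gap.
- Recompute Table 5 from that residual, labelled as 80 completers in total.
- If the 90% minimum is not met, restate comfort, vision and joint power.

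The cost is one model run on existing data and an edit to one section. No extra subjects are needed. The only downside is that the stated power may become less favourable.
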